## Blinding

*Blinding describes who is aware of the experimental manipulations within a study. Mark all that apply.*

No blinding is involved in this study.

## Study design

*Describe your study design. Examples include two-group, factorial, randomized block, and repeated measures. Is it a between (unpaired), within-subject (paired), or mixed design? Describe any counterbalancing required. Typical study designs for observation studies include cohort, cross sectional, and case-control studies.*

Sequential, non-randomized design. The BPT sample was recruited while PI [name] was at the University of Virginia. Data collection continued, led by co-PI [name], when PI [name] changed institutions to Florida State University in August, 2014. The CET sample was collected at FSU (co-PI [name] for 2015-2016, co-PI [name] for 2016-present). Identical procedures were used for both samples. Both treatments were delivered in small group format (2-4 families) or individually as needed to accommodate families' schedules. Schedule changes were accommodated to the extent possible (e.g., make-up sessions the same week). Families recruited between June 2013 and December 2014 were offered behavioral parent training (BPT). The final BPT post-treatment session was completed in June 2015. Families recruited between June 2015 and December 2016 were offered central executive training (CET). The final CET post-treatment session was completed in [TBD, likely May/June] 2017. Recruitment to CET was closed when the software for the active comparator was completed. We are currently conducting a pilot randomized trial of CET versus this active comparator (inhibition training) that is registered at clinicaltrials.gov (NCT03042338).

no file selected

## Randomization

*If you are doing a randomized study, how will you randomize, and at what level?*

Participants are not randomized because the CET intervention was in development. Recruitment to BPT was closed when CET was ready for testing. Recruitment to CET was closed when the active comparator was ready for testing.

## Analysis Plan

### Statistical models

*What statistical model will you use to test each hypothesis? Please include the type of model (e.g. ANOVA, multiple regression, SEM, etc) and the specification of the model (this includes each variable that will be included as predictors, outcomes, or covariates). Please specify any interactions that will be tested and remember that any test not included here must be noted as an exploratory test in your final article.*

#### Covariates and Data Handling

1. To describe the samples, the BPT and CET samples will be compared at pre-treatment on gender, age, SES (Hollingshead scores), WASI-II/WISC-IV Verbal Comprehension Index IQ standard scores, medication status (no/yes), race/ethnicity (US Census categories), comorbidities (no/yes), teacher reported ADHD symptoms (BASC-2 attention problems and hyperactivity T-scores), parent reported ADHD symptoms (BASC-2 attention problems, hyperactivity T-scores, CSI-IV raw severity scores for attention problems and hyperactivity/impulsivity), parent reported ODD symptoms (CSI-IV raw severity scores). Variables showing significant between-group differences at  $p = .05$  or less, corrected for multiple comparisons, will be used as covariates in all above analyses (simultaneous entry). We decided to sacrifice power if needed to control for any pre-treatment differences.
2. The CET vs. BPT pre-treatment descriptive analyses will also be conducted for the treated vs. untreated samples. For the purposes of these analyses, the BPT and CET participants will be combined as the 'treated' sample, and those who declined or otherwise were offered but did not participate in BPT and CET will be combined as 'untreated.' We will not conduct treated vs. untreated analyses separately for the BPT and CET groups due to low n. The same significance

criteria and correction for multiple comparisons will apply as for BPT vs. CET.

3. All hypothesized interactions are expected to look like Figure 1 in Redick (2015). In other words, the expected interaction pattern would be due to no pre-treatment group differences, and differential improvements favoring the group hypothesized to improve.

Unless otherwise specified below, all omnibus tests will be 2 (group; between) x 2 (variable; within) x 2 time points (pre, post; within) mixed-model ANOVA or ANCOVA. ANOVA vs. ANCOVA decision will be based on whether there are significant  $p = .05$  (or lower) group differences on any pretreatment variables as detailed in previous section. Tests that specify independent-samples or paired-samples t-tests will be run as between-group and within-group ANCOVAs, respectively, if covariate adjustments are needed based on analysis of pretreatment characteristics described in previous section.

Analyses will be run using JASP 0.8.1 (or current version).

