#### Study Timeline

Children were not randomized to treatment condition. Families recruited between June 2013 and December 2014 were offered behavioral parent training (BPT). The final BPT post-treatment session was completed in June 2015. Families recruited between June 2015 and December 2016 were offered central executive training (CET). The final CET post-treatment session was completed in [TBD, likely May/June] 2017. Recruitment to CET was closed when the software for the active comparator was completed. We are currently conducting a pilot randomized trial of CET versus this active comparator (inhibition training).

Identical procedures were used for both samples. Both treatments were delivered in small group format (2-4 families) or individually as needed to accommodate families' schedules. Schedule changes were accommodated to the extent possible (e.g., make-up sessions the same week).

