## Sample size

*Describe the sample size of your study. How many units will be analyzed in the study? This could be the number of people, birds, classrooms, plots, interactions, or countries included. If the units are not individuals, then describe the size requirements for each unit. If you are using a clustered or multilevel design, how many units are you collecting at each level of the analysis?*

The final analyzed sample size is expected to be BPT = 27, CET = 27. BPT collection is complete; the last CET group is anticipated to be complete in May/June 2017.

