#### Primary Outcomes (Working Memory)

The Rapport et al. (2009) computerized working memory tests correctly classify children with vs. without ADHD at similar rates as parent and teacher ADHD rating scales (Tarle et al., 2017), and predict hyperactivity (Rapport et al., 2009), inattention ([name] et al., 2010), and impulsivity (Raiker et al., 2012). Reliability and validity evidence includes internal consistency ( $\alpha=.82-.97$ ), 1-3-week test-retest reliability (.76-.90; Sarver et al., 2015), and expected relations with criterion working memory complex span ( $r=.69$ ) and updating tasks ( $r=.61$ )(Wells et al., under review). Six trials per set size were administered in randomized/unpredictable order (3-6 stimuli/trial; 1 stimuli/second) as recommended ([name] et al., 2016). Five practice trials were administered before each task (80% correct required). Task duration was approximately 5 (visuospatial) to 7 (phonological) minutes.

Phonological working memory. Children were presented a series of jumbled numbers and a letter (1 stimuli/second). The letter was never presented first or last to minimize primacy/recency effects, and was counterbalanced to appear equally in the other serial positions. Children reordered and recalled the numbers from least to greatest, and said the letter last (e.g., 4H62 is correctly recalled as 246H). Two trained research assistants, shielded from child view, independently recorded oral responses. Interrater reliability will be computed (% agreement = % of trials for which both RAs transcribed the identical sequence).

Visuospatial working memory. Children were shown nine squares arranged in three offset vertical columns. A series of 2.5 cm dots were presented sequentially (1 stimuli/second); no two dots appeared in the same square on a given trial. All dots were black except one red dot that never appeared first or last to minimize primacy/recency effects. Children reordered the dot locations (black dots in serial order, red dot last) and responded on a modified keyboard.

Dependent variables. Stimuli correct per trial were computed at each set size as recommended (Conway et al., 2005), and averaged to provide a single indicator for each task. Higher scores reflect better working memory.

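### The arms are not randomised, yet a baseline confounder is adjusted for only if it passes a multiplicity-corrected test, which flags a true 0.5 SD imbalance about 12% of the time under Bonferroni.

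*Combined protocol and SAP*

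**What the plan says.** Study Timeline states: "Children were not randomized to treatment condition". Study design calls it a "Sequential, non-randomized design", and Randomization agrees. The Study type item ticks the random-assignment option, but the detailed descriptions are consistent with each other and I follow them. On numbers: "The final analyzed sample size is expected to be BPT = 27, CET = 27".

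Covariates and Data Handling, item 1, lists the baseline variables on which the arms are compared. Those that differ at p = .05 "or less, corrected for multiple comparisons, will be used as covariates in all above analyses (simultaneous entry"). The stated intent follows: "We decided to sacrifice power if needed to control for any pre-treatment differences". No listed variable enters regardless of its test. Inference criteria names Bonferroni for post-hoc tests only, so the correction for this screen is not named.

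The same section applies the screen to the choice between ANOVA and ANCOVA, which rests on significant p = .05 ("or lower) group differences on any pretreatment variables as detailed in previous section". Planned t-tests become ANCOVAs "if covariate adjustments are needed based on analysis of pretreatment characteristics described in previous section".

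Some adjustment sits outside the screen. The working memory, symptom and actigraphy models contain the outcome's own pre-treatment score through the time factor. The post-hoc analyses, when triggered, regress post-treatment on pre-treatment. CSQ-8 and BTPS (Feasibility/Acceptability Outcomes) are measured only at post-treatment and have neither.

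**The concern.** A multiplicity correction limits false alarms. When confounders are screened in a non-randomised comparison, the costlier error is the miss, and a stricter threshold produces more misses. The rule therefore works against the intent stated beside it.

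The bias left by an omitted confounder depends on its imbalance and its relation to the outcome, not on its baseline p-value. For the group x time tests, the variables that matter are those related to gain. For CSQ-8 and BTPS, any variable related to the score matters, and the screen is the only route to adjustment. Because the correction is unnamed, two analysts following the plan could also fit different primary models.

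**Working it through.** The plan gives no detection rate or bias figure to reproduce, so the check starts from its inputs.

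**Inputs from the plan.** 27 per arm, so 52 degrees of freedom. Listed variables: gender, age, SES, verbal IQ, medication, race/ethnicity, comorbidity (7); two teacher BASC-2 scores, two parent BASC-2 scores, two parent CSI-IV ADHD scores and one CSI-IV ODD score (7). Total 14, counting comorbidity as one test.

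**Assumptions.** Two-sided t-tests (approximate for the four categorical variables); Bonferroni unless stated; sizes of imbalance and correlation as shown, since the plan gives none.

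**Step 1: observed gap needed to trigger adjustment.** Gap = t_crit x sqrt(2/27), with sqrt(2/27) = 0.272.
- Bonferroni: alpha = .05/14 = .00357, t_crit = 3.052, gap = 0.83 SD.
- Uncorrected: t_crit = 2.007, gap = 0.55 SD.

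**Step 2: chance that a true imbalance d is flagged.** Noncentral t with noncentrality d x sqrt(27/2); for d = 0.5 this is 1.84.

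| True imbalance | Bonferroni | Uncorrected |
|---|---|---|
| 0.3 SD | 3% | 19% |
| 0.5 SD | 12% | 44% |
| 0.8 SD | 46% | 82% |

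Other corrections at 0.5 SD, by simulation with 1 to 14 variables imbalanced and inter-correlation 0 to 0.5: Holm 12% to 16%, Benjamini-Hochberg 13% to 30%, Benjamini-Yekutieli 7% to 15%.

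**Step 3: residual bias.** With no adjustment, bias in gain SD is imbalance x correlation, for example 0.5 x 0.3 = 0.15. The screen removes only part of this. Simulation: 10,000 runs, 14 independent normal covariates, unit within-arm gain SD, gain regressed on group plus the selected covariates. With one 0.5 SD confounder, bias (type I error) is:

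| Correlation with gain | Current rule | Four-variable core plus uncorrected screen, confounder outside the core |
|---|---|---|
| 0.1 | 0.04 (5%) | 0.02 (5%) |
| 0.3 | 0.12 (7%) | 0.05 (5%) |
| 0.5 | 0.19 (11%) | 0.09 (6%) |

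For a confounder inside the core (0.5 SD, correlation 0.3), bias is 0.12 (7%) under the current rule and 0.00 (5%) with the core.

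**Step 4: scale.** If pre and post variances are equal, gain SD in score SD is sqrt(2(1 - r)). The plan reports "1-3-week test-retest reliability (.76-.90"), which gives 0.69 to 0.45, so 0.12 gain SD is about 0.08 to 0.05 score SD. That reliability covers 1-3 weeks, whereas CET runs 10 to 12 weeks, so the conversion is only a guide. For CSQ-8 and BTPS the Step 3 figures apply directly in score SD, with the correlation taken to the score.

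**Step 5: core without a screen in the primary model.** For a confounder outside the core with correlation 0.3, bias (type I error) is:

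| Imbalance | Current rule | Core only | Core plus uncorrected screen |
|---|---|---|---|
| 0.5 SD | 0.12 (7%) | 0.15 (8%) | 0.05 (5%) |
| 0.8 SD | 0.10 (7%) | 0.24 (13%) | 0.02 (5%) |

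**The case against.** The strongest reply is that the harm may be small. The middle case moves type I error from 5% to 7%, and every input to it beyond the sample size and variable list is assumed. The simulation also treats the covariates as independent. Seven of the 14 are ADHD or ODD ratings, so flagging one partly adjusts for the others. If all seven are imbalanced by 0.5 SD with inter-correlation 0.5, and one is related to gain with coefficient 0.3, bias under the current rule is about 0.06 to 0.07 and type I error 5% to 6%. This stands: the detection rates are firm under their stated assumptions, and the consequence is conditional.

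It also stands that adjustment costs power, and that a fixed core alone can be worse than the current rule (Step 5).

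Three stronger readings are tempting but not supported:
- A reader might take the second p = .05 statement, in the ANOVA/ANCOVA sentence, as a conflicting uncorrected trigger. It refers back to the earlier rule and so carries the correction with it.
- A reader might infer that baseline differences in the outcomes themselves go unadjusted. The time factor deals with these, and so do the post-on-pre ANCOVAs when triggered; CSQ-8 and BTPS are the exceptions.
- A reader might conclude that the primary comparison will be seriously biased. The documents give no imbalance or covariate-gain correlation from which that could follow.

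**Conclusion.** The concern holds as a weakness in the covariate rule. In non-randomised arms the correction cuts detection of a 0.5 SD imbalance from 44% to about 12% under Bonferroni, or to roughly 7% to 30% across other methods, contrary to the rule's own aim. The consequence ranges from negligible to moderate: about 0.04 to 0.19 gain SD of bias and 5% to 11% type I error for one independent 0.5 SD confounder correlated 0.1 to 0.5 with gain, and less if the ratings are correlated. CSQ-8 and BTPS are the most exposed. Dropping the correction alone would not be enough, since 56% of 0.5 SD imbalances would still be missed. No covariate rule can separate arm from site and calendar period. This is an inexpensive improvement, not a flaw that invalidates the analysis.

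**What to change.** In Covariates and Data Handling:

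1. The co-PIs without data access name now a small fixed core of already collected covariates, chosen as the strongest expected confounders (for example age, gender, SES, medication status and a baseline severity or comorbidity measure). Enter it in every between-group model, including CSQ-8 and BTPS, whatever the baseline p-values.
2. Keep the screen for the other listed variables without the multiplicity correction, using p <= .05 or a pre-stated standardised difference. Enter flagged variables in the primary model, with a core-only model as the sensitivity analysis. Do not confine flagged variables to a sensitivity analysis, because a core-only primary model can be more biased than the current rule.
3. Exclude an outcome's own baseline from both core and screen in its repeated-measures model.
4. Mean-centre covariates, include covariate x time terms, and make the ANOVA/ANCOVA sentence match.
5. Report baseline standardised differences, and state that site and calendar period cannot be separated from arm.

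The change is to wording only; the data are already collected. The cost is power. At an assumed 0.8 gain-SD effect with irrelevant covariates:

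| Scenario | Current rule | Core plus uncorrected screen |
|---|---|---|
| Four or five core covariates, balanced | about 82% | about 76% |
| Four core covariates, each imbalanced by 0.5 SD | about 77% | about 67% |
| Five core covariates, each imbalanced by 0.5 SD | about 77% | 63% to 65% |
| Worst case: all 14 imbalanced by 0.5 SD | 67% | 50% |

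The plan already accepts a loss of power for this purpose, and keeping the core small limits it.

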#### Primary Outcome

1. Near-transfer: 2 group x 2 task x 2 time points (pre, post). Tasks are Rapport phonological (PH) and visuospatial (VS) working memory tests. Critical test is the group x time interaction. The 2 tasks are included in the omnibus ANOVA to (1) address recommendations to probe cognitive abilities using multiple tests, and (2) maximize power for the critical group x time interaction. The 2 working memory tests are considered to tap the same 'central executive' working memory; they differ in whether that central executive is processing phonological or visuospatial information. If the group x time interaction is significant at  $p = .05$  (or lower), it will be followed by Bonferroni-corrected within-group post-hocs for each task and ANCOVA of post-treatment covaried for pre-treatment separately for each task (i.e., residualized gain scores). These post-hocs will also be performed if the main effect of time is significant (but not the group x time interaction) to allow us to better characterize change within each group (i.e., did each treatment produce significant change?). Stimuli correct per trial will be used.

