#### Secondary Outcomes

2. Far-transfer subjective ADHD symptoms: Two scales are used: the norm-referenced BASC-2 (T-scores based on age and gender norms) and CSI-IV (raw symptom severity scores). Both have separate Attention Problems and Hyperactivity/Impulsivity subscales. Both will be tested via 2 group x 2 subscale x 2 time point mixed-model ANOVA. Critical test is the group x time interaction for both. Post-hoc plan follows #1 above.

3. Far-transfer objective (proximal) ADHD symptoms: Same 2 group x 2 task (PH-actigraphy, VS-actigraphy) x 2 time points approach as above; same post-hoc plan. Critical test is the group x time interaction. Actigraph data will be PIM intensity scores collected while the child was completing the PH and VS tests described above. Each data point reflects total hyperactivity score (Rapport et al., 2009), which is computed by summing the PIM activity counts for each of the 3 actigraphs (non-dominant wrist, left ankle, right ankle).

4. Far-transfer objective (distal) ADHD symptoms: Same 2 group x 2 task (PaintBeginning-actigraphy, PaintEnd-actigraphy) x 2 time points approach as above; same post-hoc plan. Critical test is the group x time interaction. Actigraph data will be PIM intensity scores collected while the child was completing the beginning of session and end of session Paint activity (drawing using Microsoft Paint). Each data point reflects total hyperactivity score (Rapport et al., 2009), which is computed by summing the PIM activity counts for each of the 3 actigraphs (non-dominant wrist, left ankle, right ankle).

5. Far-transfer subjective oppositional-defiant symptoms: Included as fidelity check based on evidence that BPT may produce greatest effects on oppositional defiant symptoms. Analysis will be 2 group x 2 timepoints mixed-model ANOVA (only one measure of ODD symptoms was collected). Critical test is the group x time interaction. CSI-IV raw symptom scores for the ODD dimension will be used as dependent variable. Bonferroni-corrected paired-sample t-tests for each group separately (pre vs. post), and between-group at post covaried for pre-treatment ODD symptoms are tested because of compelling evidence that BPT improves these symptoms (manipulation check; if no significant reductions in BPT group, may indicate limited BPT efficacy).

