## Follow-up analyses

*If not specified previously, will you be conducting any confirmatory analyses to follow up on effects in your statistical model, such as subgroup analyses, pairwise or complex contrasts, or follow-up tests from interactions? Remember that any analyses not specified in this research plan must be noted as exploratory.*

Planned contrasts/post-hocs are described under the statistical model question above. Unless otherwise specified, significant main effects/interactions in the omnibus model will be followed by Bonferroni-corrected post hocs/contrasts to characterize the omnibus effects.

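### When only the time effect is significant, the plan still tests the per-task between-group ANCOVAs, although that branch is meant to describe change within each group

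*Combined protocol and SAP*

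**What the plan says.** Statistical models, Primary Outcome, item 1 (worded almost identically under Hypotheses) makes the group x time interaction the critical test. If it is significant, the follow-up is "Bonferroni-corrected within-group post-hocs for each task and ANCOVA of post-treatment covaried for pre-treatment separately for each task". The next sentence opens a second route to the same set: "These post-hocs will also be performed if the main effect of time is significant (but not the group x time interaction". The reason given is "to allow us to better characterize change within each group (i.e., did each treatment produce significant change".

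Secondary Outcomes carries the rule over to the parent ADHD ratings in item 2 ("Post-hoc plan follows #1 above") and to both actigraphy analyses in items 3 and 4 ("x 2 time points approach as above; same post-hoc plan").

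Three other places bear on how these tests would be read:

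- Follow-up analyses says that follow-ups are Bonferroni-corrected and serve to characterise the omnibus effects.
- Inference criteria applies Bonferroni to post-hoc tests, leaves omnibus tests uncorrected, and counts p of .05 or lower as a significant effect.
- Recommended elements (item 1 under Hypotheses, item 10 under Statistical models) expects this ANCOVA to show the group difference if the arms differ before treatment. It then says that finding no difference indicates equivalence.

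**The concern.** The second route tests something that its stated purpose does not ask for. Whether each treatment produced change is answered by the pre-post test within each arm. A between-group ANCOVA answers a different question, the one on which the critical test has just failed. The gate does not help either, because a time effect pooled over arms is no evidence that the arms differ.

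At stake is a second chance at a between-group claim. For working memory and actigraphy, where the plan predicts that CET does better, a null interaction could be followed by a significant difference on one task. For the parent ADHD ratings the plan predicts improvement in both arms. If they improve equally, time without interaction is the expected result, so the fallback is the route most likely to be used. There, a non-significant ANCOVA could be read as equivalence, which bears directly on the non-inferiority question in research question 3.

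**Working it through.** The plan gives no error rate or power figure for this point, so there is nothing to reproduce.

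**Step 1. What each route triggers (primary outcome).**

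- Interaction significant: 2 arms x 2 tasks = 4 within-group tests, plus 2 ANCOVAs.
- Interaction not significant, time significant: the same 6 tests. The stated purpose uses only the 4 within-group tests.

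**Step 2. Why the gate is uninformative.** Let C and B be the mean changes in CET and BPT, averaged over the two tasks. The time effect is (C + B)/2 and the interaction is C - B. The first can be large while the second is exactly zero.

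**Step 3. Chance of a false between-group claim.** With no true group difference,

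P(any claim) = P(interaction significant) + P(interaction not significant, time significant, smaller ANCOVA p at most .05/k).

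The family is not defined, so k = 2 (the two ANCOVAs), 4 (the size of the within-group set) and 6 (all tests) were each tried. The per-test levels are .05/2 = .025, .05/4 = .0125 and .05/6 = .0083.

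Inputs from the documents:

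- 27 per arm (Sample size).
- Pre-post correlation r of .76 to .90, from the 1-3-week test-retest reliability (Primary Outcomes, Working Memory), used as a proxy.

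Assumptions:

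- Between-task correlation of .3 to .7.
- A time effect common to both arms.
- Two-sided tests; sidedness is not stated.
- No baseline gap, except in step 4.

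Example cells from simulation (40,000 trials each; Monte Carlo error about 0.2 points):

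| r | Between-task r | Time effect | Interaction significant | Time significant | Added by fallback, k = 2 / 4 / 6 | Any claim, k = 2 / 4 / 6 |
|---|---|---|---|---|---|---|
| .76 | .3 | 0 | 4.88% | 4.8% | 0.13 / 0.06 / 0.03 | 5.02 / 4.94 / 4.92% |
| .76 | .3 | 0.3 SD | 5.00% | 97.2% | 2.49 / 1.03 / 0.60 | 7.49 / 6.04 / 5.61% |
| .90 | .7 | 0.5 SD | 4.90% | 100% | 1.30 / 0.34 / 0.16 | 6.20 / 5.24 / 5.06% |

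Over all runs at 0.3 to 0.5 SD, the totals span about 6.2-8.0% (k = 2), 5.2-6.5% (k = 4) and 5.0-6.0% (k = 6). These count claims in either direction.

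**Step 4. Baseline gap.** Allocation was sequential and non-randomized. Working memory and actigraphy scores are not among the pre-treatment variables screened as covariates (Covariates and Data Handling). Suppose the arms differ stably at baseline by g and change equally. The interaction then stays valid, but the ANCOVA contrast is shifted by about (1 - r) x g towards the arm with the higher baseline. For an assumed g of 0.5 SD, the shift is 0.24 x 0.5 = 0.12 SD at r = .76 and 0.10 x 0.5 = 0.05 SD at r = .90. Simulated with a 0.4 SD time effect, any false claim at k = 2 is then about 9-13%, with the interaction still near 5%.

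**Step 5. What a null ANCOVA can show.** With 2 x 27 - 3 = 51 degrees of freedom, the 95% half-width is about 2.01 x sqrt(2(1 - r^2)/27) SD, ignoring any baseline gap. That is 0.36 SD at r = .76 and 0.24 SD at r = .90. The documents give no pre-post correlation for the parent ratings; at an assumed .4 to .7 it is 0.50 to 0.39 SD. A non-significant result is therefore compatible with sizeable differences.

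**The case against.** The strongest defence is that these tests do have a status. They are called post-hocs, they sit below a named critical test, and three sections require Bonferroni correction. Follow-up analyses says that follow-ups characterise omnibus effects, and nowhere does the plan say that a fallback ANCOVA overrides a null interaction. All of that stands, and it rules out several stronger readings that a reader might infer:

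- **That the ANCOVAs are confirmatory.** The form asks "will you be conducting any confirmatory analyses to follow up on effects in your statistical model" and the answer is "Planned contrasts/post-hocs are described under the statistical model question above". The word confirmatory belongs to the form's standard question; the answer does not promote the tests beyond planned post-hocs.
- **That the ANCOVAs are uncorrected.** In item 1 the correction is named only before the within-group tests, but Recommended elements, Follow-up analyses and Inference criteria extend it to post-hocs in general. An uncorrected error rate would not describe this plan.
- **That item 5 shares the defect.** Its between-group ODD comparison has no gate, but the plan labels it a fidelity and manipulation check, so its role is stated.

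The size also depends on the reading and the scenario. Recommended elements gives the ANCOVA weight for superiority only if the arms differ before treatment. If a fallback ANCOVA counts only when that task's baseline differs at p of .05 or lower, the fallback adds just 0.1-0.2 points at divisor 2. The shared time effect is an assumption too. BPT is not expected to improve working memory, and Procedures says that retest effects, if present, would favour BPT. With an assumed extra 0.1 SD gain in BPT and a 0.3 SD time effect, all false claims favouring CET, interaction included, fall to 0.3-0.9% at divisor 2.

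Finally, reading a null as equivalence is a fault wherever this ANCOVA is run, not one that the time-only gate creates.

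What survives is narrow. Inference criteria attaches no baseline condition when it calls a corrected result significant, and no passage bars a between-group claim from this branch. The branch is also where the equivalence reading would most often be applied.

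**Conclusion.** The point holds as a mismatch between a stated rule and its stated purpose. The time-only branch runs between-group tests that it does not need, after the critical between-group test has failed, and the plan's own criteria would let either outcome be interpreted.

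The inflation for working memory is modest: from about 5% to about 6.2-8.0%, 5.2-6.5% or 5.0-6.0% at divisors 2, 4 and 6. This rests on an assumed shared time effect of 0.3 to 0.5 SD, an assumed between-task correlation of .3 to .7, no baseline gap and the cited reliability as pre-post correlation. It vanishes without a time effect and grows to about 9-13% (divisor 2) under an assumed 0.5 SD baseline gap. For actigraphy and the parent ratings the documents give no pre-post correlation, so no rate is claimed. For the parent ratings the main risk is the reading of a null result.

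The documents do not support saying that a null interaction will be overridden, or that the ANCOVAs lack any status. The undefined Bonferroni family is missing detail, not an error in itself. The point is worth correcting before analysis.

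**What to change.** - In Hypotheses and Statistical models, Primary Outcome, item 1, and so in items 2 to 4: if only time is significant, test only the Bonferroni-corrected within-group changes. Report the per-task ANCOVAs there as estimates with confidence intervals, and state that they do not alter the verdict of the critical test.
- In Recommended elements (item 1 under Hypotheses, item 10 under Statistical models): state that a non-significant ANCOVA is not evidence of equivalence, and that an ANCOVA after a null interaction does not support superiority.
- As a clarification, state the Bonferroni family.

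The edit is a few sentences. Its cost is that an effect confined to one task could not be claimed after a null interaction. For an assumed 0.5 SD effect on one task, with a 0.4 SD time effect and r of .76 to .90, the chance of claiming it falls from 69-97% to 29-71% at divisor 2, and from 52-92% to 28-70% at divisor 6. For an effect on both tasks the loss is small: at 0.3 SD, from 46-87% to 40-85% (divisor 2). The plan treats the two tasks as tapping one central executive construct. On that rationale the two-task case is the relevant one and the cost matters little.
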